**Listing 16.2.4.3.1 Laboratory Data – Haematology – Enrolled Set**

**Listing 16.2.4.3.2 Laboratory Data – Biochemistry – Enrolled Set**

**Listing 16.2.4.3.3 Laboratory Data – Coagulation – Enrolled Set**

**Listing 16.2.4.3.4 Laboratory Data – Thyroid Function – Enrolled Set**

Safety laboratory test results will be listed.

**Listing 16.2.4.3.5 Laboratory Data – Clinically Significant Urinalysis Results (Local Dipstick) – Enrolled Set**

All clinically significant urinalysis (local dipstick) data will be listed by treatment group.

**Listing 16.2.4.3.6 Laboratory Data – Signs of Hyponatraemia – Enrolled Set**

All patients with signs of hyponatraemia will be listed by treatment group.

**Listing 16.2.4.3.7 Laboratory Data – Urinalysis Results (Central Laboratory) – Enrolled Set**

All urinalysis (provided by central laboratory) data will be listed by treatment group.

**Listing 16.2.4.3.8 Pregnancy Tests – Enrolled Set**

Urine and serum pregnancy test results will be listed by treatment group for female patients, including cases when test was not done.

### **5.6.3 Vital Signs**

Vital signs (tympanic body temperature, systolic and diastolic blood pressure and pulse rate) after five minutes at rest are collected at V1a, V2, V3, V5, V7, EOT, EDV and, if applicable, UNS.

Results for tympanic body temperature, systolic and diastolic blood pressure and pulse rate will be classified according to whether the value was lower than (L), within (N) or higher than (H) the reference range for that parameter. The normal ranges are provided in Table 4.

**Table 4: Normal Ranges for Vital Signs**

Parameter	Lower Reference Range	Upper Reference Range
Tympanic body temperature	36.0	38.5
Systolic blood pressure [mmHg]	80	160
Diastolic blood pressure [mmHg]	50	110
Pulse rate [bpm]	50	100

Clinical significance (not significant/significant) of vital sign abnormalities will be assessed by the investigator.

The following statistical output will be provided:

**Table 15.3.3.1.1 Summary of Vital Signs – Safety Set**

Vital sign parameters will be summarised including change from baseline at each visit slot where assessments were made by treatment group and in total.

**Table 15.3.3.1.2 Incidence of Vital Signs Abnormalities – Safety Set**

The number and percentage of patients with Low, Normal and High categories of each vital sign parameter will be displayed by treatment group and in total. Percentages will be based on the number of patients at the specified visit slot.

**Listing 16.2.4.4 Vital Signs – Enrolled Set**

Vital signs data will be listed.

### **5.6.4 12-Lead Electrocardiogram Data**

A standard 12-lead electrocardiogram (ECG) is performed at V1a, V2, V3, EDV (if EDV performed before V3) and, if applicable, UNS.

If an ECG was done after primary stroke, the results will be used and the examination does not need to be repeated at V1a. ECG assessment after primary stroke, if available, otherwise the last collected value before IMP intake will be defined as baseline value.

ECG results will be assessed by an investigator if normal, abnormal or CS abnormal and assessments will be documented in the eCRF.

The following statistical outputs will be presented:

**Table 15.3.3.2 Summary of ECG Assessments – Safety Set**

The number and percentage of patients with normal, abnormal, and CS abnormal ECG assessments will be displayed by treatment group and in total. Percentages will be based on the number of patients at the specified visit slot.

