8. a. Patient is able to give informed consent and to write and has signed a written informed consent OR
b. Patient is able to give informed consent, but unable to write and has provided verbal witnessed consent.

Exclusion criteria:

(as per patient interview, medical records or reported by family members)

Patients are to be excluded from the trial for ANY ONE of the following reasons:

1. Contraindication to ESL, i.e. known hypersensitivity to ingredients of ESL formulation or other carboxamide derivatives (e.g., oxcarbazepine, carbamazepine), or second or third degree atrioventricular (AV) block not corrected with a permanent pacemaker.
2. Known Han Chinese or Thai ancestry.
3. History of previous stroke (other than the one described in inclusion criteria no. 2 - 3).
4. Sinus venous thrombosis.
5. Spontaneous sub-arachnoid haemorrhage due to e.g. aneurysmatic or arteriovenous malformation.
6. History of USs prior to primary stroke.
7. Impaired pre-stroke level of function, i.e. modified Rankin Scale (mRS) score > 3 prior to first stroke occurrence.
8. History of AED use before primary stroke within the last 5 years as defined in the list of not allowed AEDs.
9. Use of ESL, unless provided as IMP of this trial, and oxcarbazepine.
10. Severe hepatic impairment.
11. Estimated glomerular filtration rate (eGFR) < 30 mL/min/1.73 m² (measured at V1a).
12. Known or suspected acute or chronic alcoholism, delirium tremens, or toxic psychosis.
13. History of suicidal ideation or suicide attempt within the past 3 years.
14. Presence of any other significant or progressive/unstable medical condition that, in the opinion of the investigator, would compromise evaluation of the trial treatment or may jeopardise the patient's safety, compliance or adherence to protocol requirements, such as significant psychiatric, cardiovascular, respiratory, metabolic, endocrine, haematologic, infectious or neurological disease.
15. For women: Pregnancy or breast-feeding.
16. Previous enrolment in this trial or participation in any other investigational drug trial within the past 30 days (or 5 half-lives of IMP whichever is longer) prior to V1a.
17. Persons committed to an institution by virtue of an order issued either by the judicial or other authorities.

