**Urinalysis:**

- local: pH, specific gravity, protein, blood, glucose, ketones, bilirubin, urobilinogen, leukocytes, nitrite (local dipstick). Microscopy and other appropriate tests (as needed) will be performed if dipstick indicates any significant abnormality.
- central: U-Casts, U-Crystals, U-Epithelials, U-Erythrocytes quan., U-Leucocytes quan., U-Others.

**Urine pregnancy tests:** in females of childbearing potential.

All laboratory values will be classified as normal or abnormal according to the laboratories' normal ranges and as clinically significant (yes/no) according to the assessment of the investigator.

The following statistical outputs will be provided:

[Table 15.3.2.1.1 Summary of Clinical Laboratory Tests: Haematology – Safety Set](#)

[Table 15.3.2.1.2 Summary of Clinical Laboratory Tests: Biochemistry – Safety Set](#)

[Table 15.3.2.1.3 Summary of Clinical Laboratory Tests: Coagulation – Safety Set](#)

The default summary statistics of clinical laboratory test results for haematology, biochemistry (including eGRF) and coagulation will be presented by treatment group and in total by visit slots (if applicable) at V1, baseline, V3, EDV (if applicable) and Endpoint. The absolute change from baseline will be presented as well.

[Table 15.3.2.2.1 Clinical Laboratory Tests: Incidence of Haematology Abnormalities – Safety Set](#)

[Table 15.3.2.2.2 Clinical Laboratory Tests: Incidence of Biochemistry Abnormalities – Safety Set](#)

[Table 15.3.2.2.3 Clinical Laboratory Tests: Incidence of Coagulation Abnormalities – Safety Set](#)

The number and percentage of patients with Low, CS Low, Normal, High, and CS High categories of each laboratory parameter will be displayed by treatment group and in total. Percentages will be based on the number of patients at the specified visit slot.

[Table 15.3.2.3.1 Clinical Laboratory Tests: Shift Table of Haematology Results from Baseline to Endpoint – Safety Set](#)

[Table 15.3.2.3.2 Clinical Laboratory Tests: Shift Table of Biochemistry Results to Endpoint – Safety Set](#)

[Table 15.3.2.3.3 Clinical Laboratory Tests: Shift Table of Coagulation Results to Endpoint – Safety Set](#)

Shift tables showing changes in the number and frequency of patients with respect to the normal range and clinical significance between baseline and endpoint by treatment will be provided. Patients with missing data will be presented as part of a “missing” category.

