**Listing 16.2.4.5 Lead ECG Assessments – Enrolled Set**

12-lead electrocardiogram findings will be listed.

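### The only ECG table counts ratings visit by visit, so it cannot show within-patient worsening; a new abnormality that is neither rated clinically significant nor reported as an AE gets no count by arm

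*SAP*

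**What the plan says.** SAP 5.6.4 sets the schedule: "A standard 12-lead electrocardiogram (ECG) is performed at V1a, V2, V3, EDV (if EDV performed before V3) and, if applicable, UNS". The recorded variable is a three-level rating: "ECG results will be assessed by an investigator if normal, abnormal or CS abnormal and assessments will be documented in the eCRF". No interval and no type of finding is specified for summary.

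Table 15.3.3.2 is the only ECG table in the text and in the SAP 10.1 index. Its content is described as follows: "The number and percentage of patients with normal, abnormal, and CS abnormal ECG assessments will be displayed by treatment group and in total". Its denominator is set visit by visit: "Percentages will be based on the number of patients at the specified visit slot". The only other ECG output is Listing 16.2.4.5: "12-lead electrocardiogram findings will be listed".

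SAP 5.6.4 also defines a baseline: "ECG assessment after primary stroke, if available, otherwise the last collected value before IMP intake will be defined as baseline value". No ECG output is described as calculating change or shift from it. SAP 4.8 gives a different general rule for variables other than the efficacy scales: the last non-missing value before first IMP intake.

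Laboratory data are treated differently in SAP 5.6.2 (Tables 15.3.2.3.1 to 15.3.2.3.3): "Shift tables showing changes in the number and frequency of patients with respect to the normal range and clinical significance between baseline and endpoint". Tables 15.3.2.4.1 to 15.3.2.4.3 repeat this for the worst post-baseline value.

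Under SAP 4.5, each visit slot takes the non-missing assessment, scheduled or unscheduled, that lies closest to the target day.

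**The concern.** The ECG is a named safety endpoint in both documents. The protocol synopsis (exclusion criterion 1) lists as a contraindication to ESL "second or third degree atrioventricular (AV) block not corrected with a permanent pacemaker", so new conduction disturbance is one foreseeable finding among those the endpoint should be able to count.

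Patients enter within days of a stroke, and some will plausibly have an abnormal ECG at entry. In that setting the useful safety quantity is how many patients per arm got worse after starting IMP. Separate per-visit totals do not give that number, and a patient who is rated abnormal both before and after a new finding changes no cell. At stake is whether the report can state a by-arm count of treatment-emergent ECG worsening, or whether a reader must assemble it from a listing.

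**Working it through.** The documents state no ECG figure, so there is none to reproduce. The check has four steps. All patient counts below are assumptions. The 100 per arm is the planned arm size (SAP 2.6), and recruitment stopped before it was reached.

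**1. What per-visit totals can identify.** Label the ratings 0 = normal, 1 = abnormal, 2 = CS abnormal. Let n_ij be the number of patients moving from rating i at baseline to rating j at V2. The table prints only the baseline totals n_0., n_1., n_2. and the V2 totals n_.0, n_.1, n_.2. The number who worsened is W = n_01 + n_02 + n_12. Two limits apply:
- worsened patients end in category 1 or 2, so W ≤ n_.1 + n_.2;
- they start as normal, or move from abnormal to CS, so W ≤ n_0. + n_.2.

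The largest possible W is the smaller of the two. Listing every compatible 3×3 table for four examples of 100 patients gave:

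| Baseline (normal/abnormal/CS) | V2 | Upper limit | Range of W |
|---|---|---|---|
| 50/45/5 | 50/45/5 | min(50, 55) = 50 | 0 to 50 |
| 70/27/3 | 70/27/3 | min(30, 73) = 30 | 0 to 30 |
| 30/60/10 | 30/60/10 | min(70, 40) = 40 | 0 to 40 |
| 50/45/5 | 55/41/4 | min(45, 54) = 45 | 0 to 45 |

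In the last row the totals improve, yet up to 45 patients could have worsened. The examples take the same 100 patients at both visits. In the trial the denominator is whoever has an ECG in the slot, so differences between visits also mix in drop-out.

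**2. Slotting.** SAP Table 3 gives V2 a target of Day 8 and a range of Days 2 to 31. Take a scheduled ECG on Day 8 (distance 0) and an abnormal unscheduled ECG on Day 15 (distance 15 − 8 = 7). The Day 8 ECG is used and the Day 15 ECG is left out, even if rated CS. V2 carries most of the weight: V3 is nominally Day 38, after planned last intake on Day 30 or Day 37 (SAP 2.5), so on nominal days V2 is the only scheduled post-baseline ECG on treatment.

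**3. Where a new finding is counted.**
- Rated CS on the slotted ECG: the patient moves category in Table 15.3.3.2, although an opposite move can offset it.
- Reported as an AE: counted by arm under SOC and preferred term (SAP 5.6.1; TEAEs cover onset or worsening up to 14 days after last IMP intake).
- Neither, and normal before: adds to the abnormal total, but is not identified as new.
- Neither, and abnormal before: moves nothing in the table; only the listing could show it.

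**4. Baseline.** Every trial ECG is taken after the primary stroke, so the first clause of the 5.6.4 rule neither chooses among several ECGs nor says that the one chosen must precede IMP. SAP 4.8 does both. The two rules can pick different ECGs.

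**The case against.** A reader might infer that a new conduction disorder in a patient already rated abnormal is invisible in the plan as a whole. The documents do not support that. The TEAE tables count reported events by arm and preferred term, serious TEAEs and those leading to IMP discontinuation have their own tables, and a CS rating changes category. To escape every by-arm count of new findings, a new AV block would have to be judged not clinically significant and also go unreported as an AE. What remains is narrower: SAP 5.6 names physical and neurological findings as part of TEAEs and does not name ECG findings, although nothing excludes them.

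A reader might also infer that resolving post-stroke abnormalities will cancel new ones and leave the arms looking equal. Randomisation answers much of this. Assume 100 per arm with 50 not normal at baseline. If 3 resolve in each arm and 3 are new on ESL only, the table shows 50 − 3 + 3 = 50 (50.0%) on ESL and 50 − 3 = 47 (47.0%) on placebo, so the excess is visible. Equality needs something further, such as 6 resolving on ESL: 50 − 6 + 3 = 47. The between-arm comparison is therefore informative, but it estimates a net difference and not the number who worsened.

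Two more objections stand in part. Physical and neurological findings are also tabulated by category without shifts, so ECG is not singled out. And a shift table alone still leaves abnormal-to-abnormal changes in one cell. The unseen table and listing shells and the full protocol could settle whether the type of ECG finding is recorded and when it must be reported as an AE.

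**Conclusion.** The point holds in a limited form. Table 15.3.3.2 cannot show within-patient worsening, slotting can remove an abnormal unscheduled ECG from it, and the ECG baseline in 5.6.4 feeds no described change or shift output, although the same SAP provides both kinds of shift table for laboratory data. A new abnormality that is neither rated CS nor reported as an AE has no by-arm count as a new event.

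The size cannot be stated from the documents. The 0 to 50 in 100 range illustrates what the totals leave open under assumed counts; it is not an estimate of what happened. The conclusion rests on the structure of the outputs and not on arm size or the share abnormal at baseline. Efficacy is unaffected. This is a desirable improvement to a safety summary, not a serious defect.

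**What to change.** Amend SAP 5.6.4 before unblinding as follows.

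1. **Shift table.** Add a by-arm table (Safety Set) of the ECG rating from baseline to V2, and from baseline to the worst post-baseline rating up to V3 or EDV. The worst rating takes in all unscheduled ECGs in that period and is not restricted to the slotted one. Show a missing category, as the laboratory shift tables do.
2. **Baseline.** State that the ECG baseline is the last assessment before first IMP intake, so that 5.6.4 agrees with 4.8.
3. **New conduction findings.** Add by-arm counts of patients with new AV-block or other conduction findings, from a list of AE preferred terms fixed before unblinding. Add the recorded ECG findings only if the eCRF holds their type. This part is needed because the shift table does not separate abnormal-to-abnormal changes.

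The cost is one extra descriptive table plus a check of what the eCRF holds. The shift table uses ratings already collected and needs no new ECG or reader. If the eCRF holds only the rating, the conduction count rests on AE terms alone, and a footnote should say so.

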**Listing 16.2.4.5 Lead ECG Assessments – Enrolled Set**

12-lead electrocardiogram findings will be listed.

**5.6.5 Physical and Neurological Examination Findings**

Physical examinations are performed at V1a, V2, V3, V5, V7, EOT, EDV and, if applicable, UNS on relevant body systems (appearance, skin, eyes, ears-nose-throat, lungs-chest, heart, abdomen, extremities, other).

Neurological examinations are performed at V1a, V2, V3, V5, V7, EOT, EDV and, if applicable, UNS. Complete neurological examination will include mental status, cranial nerves, motor system, sensory system, reflexes, co-ordination, gait and station.

Physical and neurological examination findings will be assessed by an investigator if normal or abnormal and if abnormal, clinical significance (significant/not significant) will be assessed.

The following statistical outputs will be presented:

**Table 15.3.3.3 Summary of Physical Examination Findings – Safety Set**

The number and percentage of patients with normal, abnormal, and CS abnormal physical examinations findings will be displayed at all visits by treatment group and in total. Percentages will be based on the number of patients at the specified visit slot.

**Table 15.3.3.4 Summary of Neurological Examination Findings – Safety Set**

The number and percentage of patients with normal, abnormal, and CS abnormal neurological examinations findings will be displayed at all visits by treatment group and in total. Percentages will be based on the number of patients at the specified visit slot.

**Listing 16.2.4.6 Physical Examination Findings – Enrolled Set**

Physical examination findings will be listed.

**Listing 16.2.4.7 Neurological Examination Findings – Enrolled Set**

Physical examination findings will be listed.

**5.6.6 Analysis of Exploratory Endpoint**

Recording of the Electroencephalogram (EEG) is optional. All EEG analyses will be presented for the EEG analysis subset.

EEG will be performed at V1a, EOT and, if applicable, UNS. If an examination was done after primary stroke, the results will be used, and the examination does not need to be repeated at V1a.

EEG parameters will be evaluated exploratively using descriptive statistics and provided in a separate report.

## **6. BLIND DATA REVIEW**

A BDR will be performed after data entry and following a database lock. The following goals are defined for the BDR:

- to identify major/minor protocol deviations
- to identify patients that are not eligible for the per protocol population
- to identify protocol deviations that may affect the primary endpoint, i.e. patients with insufficient IMP compliance, patients with intake of prohibited medications during the observation period
- to discuss any open data issues

All decisions made during the BDR will be documented in the BDR report before the closure of the database and the randomisation code release.

An appropriate clinical study team, including a physician, will review potential protocol deviations and relevant information regarding those deviations to determine a possible impact on efficacy endpoints. An assessment will be made as to the effect of each of the possible deviations to determine if it is considered major or minor. The status, major or minor, of each protocol deviation will be documented in the BDR report. A patient may have one or more major protocol deviations resulting in the exclusion of that patient from the per-protocol analysis set.

Protocol deviations will, if possible, be validated against data recorded in the eCRF. Where an answer for an inclusion/exclusion tick box differs from the algorithmic check of the criteria, the algorithmic check will overrule the tick box.

Protocol deviations of the following categories will be reviewed during the BDR.

### **Inclusion Criteria**

No.	Inclusion Criteria Deviation	Major/ Minor/ Case by case review
PD#01.	1. Male or female patient not aged 18 years and above.	

No.	Inclusion Criteria Deviation	Major/ Minor/ Case by case review
PD#02.	2a. CTP V3.0: To not have one of the following confirmed by magnetic resonance imaging (MRI)/computed tomography (CT): 

• Acute ischaemic or intracerebral haemorrhagic stroke with

- an acute symptomatic seizure until 120 hours post-stroke and

- cerebral cortex involvement OR

• Acute ischaemic stroke with

- National Institutes of Stroke Scale (NIHSS) <math>\geq 11</math> and

- cerebral cortex involvement and

- large-artery atherosclerosis and/or territory of middle cerebral artery (MCA) OR

• Acute ischaemic stroke with

- NIHSS 4-10 and

- cerebral cortex involvement and

- large-artery atherosclerosis and

- territory of MCA OR

• Acute intracerebral haemorrhagic stroke with

- cerebral cortex involvement and

- volume of intracerebral haemorrhage <math>> 10</math> mL.

	
	2b CTP V2.0: Acute intracerebral haemorrhage with a CAVE score $\geq 3$ or acute ischaemic stroke with a SeLECT score $\geq 6$ , in each case confirmed by magnetic resonance imaging computed tomography	
PD#03.	CTP 2.0: Time of stroke occurrence is known and V1b is not planned within 96 hours. CTP 3.0. Time of stroke occurrence is known and V1b is not planned within 120 hours since the known time of stroke occurrence, or since last time seen well.	
PD#04.	Brain scan analysis has reliably excluded structural e.g. cerebral tumour or brain abscess, etc. brain lesions that can mimic stroke,	
PD#05.	a. Patient is not able to give informed consent and to write and has not signed written informed consent OR b. Patient is not able to give informed consent, and unable to write and has provided verbal witnessed consent OR c. Patient is unable to give informed consent, and not likely to regain this ability until V2, and the informed consent is not deferred OR d. Patient is unable to give informed consent, but likely to regain this ability until V2, but patient's legal representative (according to the respective national/local requirements) has noz provided written informed consent.	

No.	Inclusion Criteria Deviation	Major/ Minor/ Case by case review
PD#06.	Female patients without childbearing potential (2 years postmenopausal, bilateral oophorectomy or tubal ligation, or complete hysterectomy) are eligible. Female patients with childbearing potential must not be pregnant as confirmed by a negative pregnancy test and sexually active females must use a medically acceptable effective nonhormonal method of contraception up to the end of the current menstrual cycle after stopping treatment. Acceptable methods for women are surgical intervention (e.g. bilateral tubal occlusion), intrauterine device, double-barrier methods, true sexual abstinence (i.e. when this is in line with the preferred and usual lifestyle of the patient) and vasectomised male partner, provided that he is the sole partner of that patient. Periodic abstinence (e.g., calendar, ovulation, symptothermal, post-ovulation methods) and withdrawal are not acceptable methods of contraception.	
PD#07.	V1b is within 96 hours (CTP 2.0) / 120 hours (CTP 3.0) after stroke occurrence.	
PD#08.	Inclusion criteria at V2 (only applicable for patients who were unable to give informed consent at V1a.) 8. a. Patient is able to give informed consent and to write and has signed a written informed consent OR b. Patient is able to give informed consent, but unable to write and has provided verbal witnessed consent.	

